2.1.3.1 Severe Exacerbation Events

A severe exacerbation event during the study is defined as any of the following:

- Use of systemic corticosteroids for \geq 3 days.
 - At least double the dose of systemic corticosteroids for patients enrolling from EFC13691 who are currently on systemic corticosteroids.
- Or, hospitalization or emergency room visit because of asthma, requiring a systemic corticosteroid treatment.

The severe exacerbation events are collected on eCRF page "Asthma exacerbations event". Only events confirmed on eCRF page will be used in the analysis.

Both number and annualized rate of severe exacerbation events will be analyzed. The annualized event rate is defined as the number of severe exacerbation events per patient-year. Number and annualized rate will also be analyzed for severe exacerbation with use of systemic corticosteroids for \geq 3 days only, and that with hospitalization or with emergency room visit only. The mean duration of a severe exacerbation will also be summarized.

For the treatment period, total number of events and standardized on-treatment duration will be calculated for each patient:

• The total number of events is defined as the number of events that are onset between the date of first IMP dose in LTS12551 study and the date of last IMP dose in LTS12551 study + 14 days;

The standardized on-treatment duration (in years) is calculated by (the date of last IMP dose in LTS12551 study – the date of first IMP dose in LTS12551 study + 14 days)/365.25.

2.1.3.2 Forced expiratory volume in one second (FEV1) and other spirometry assessments

The forced expiratory volume in one second (FEV1) is part of the spirometry assessment that will be performed at Visit 1, Visit 3 (Week 2), Visit 4 (Week 4), Visit 6 (Week 8), Visit 8 (Week 12), Visit 11 (Week 24), Visit 13 (Week 48; if applicable), Visit 15 (Week 72; if applicable), Visit 16 (Week 84; if applicable), Visit 17 (End-of-Treatment) and Visit 18 (End-of-Study). The other parts of the spirometry assessment, including the percent predicted FEV1, Forced Vital Capacity (FVC) and Forced Expiratory Flow (FEF) 25-75%, will be performed at the same visits as above.

A spirometer that meets the 2005 American Thoracic Society (ATS) / European Respiratory Society (ERS) recommendations will be used. The ATS/ ERS Standardization of Spirometry should be used as a guideline (1). Spirometry should be done at the study site approximately the same time of the day (preferably in the morning, but it could be done at a different time of the day). Spirometry will be performed after a washout period of bronchodilators according to their action duration (for example, withholding the last dose of salbutamol/albuterol or levosalbutamol/levalbuterol for at least 6 hours and withholding the last dose of LABA for at least 12 hours [ultra-LABA like vilanterol should be withheld for at least 24 hours] and withholding the last dose of LAMA for at least 24 hours). Also spirometry should be performed prior to IMP administration, as applicable.

Pulmonary function tests will be measured in the sitting position and the highest measure will be recorded in liters for FEV1.

2.1.3.3 Asthma control questionnaire, 5-question version (ACQ-5)

The ACQ-5 was designed to measure both the adequacy of asthma control and change in asthma control which occurs either spontaneously or as a result of treatment.

The ACQ-5 has 5 questions, reflecting the top-scoring five asthma symptoms: woken at night by symptoms, wake in the mornings with symptoms, limitation of daily activities, shortness of breath and wheeze. Patients are asked to recall how their asthma has been during the previous week and to respond to the symptom questions on a 7-point scale (0=no impairment, 6= maximum impairment) (see Appendix F).

A global score is calculated: the questions are equally weighted and the ACQ-5 score is the mean of the 5 questions and, therefore, between 0 (totally controlled) and 6 (severely uncontrolled). Higher score indicates lower asthma control. On the 7-point scale of the ACQ-5, a change or difference in score of 0.5 is the smallest that can be considered clinically important, corresponding to the Minimal Clinically Important Difference (MCID) defined by the developer.

In addition, the minimal clinically important difference at patient level (pMCID) is the smallest treatment efficacy that would lead to a change in a patient's management; and, the minimal clinically important difference at group mean level (gMCID) is the smallest treatment efficacy that would lead to a change in a group's management. The threshold of gMCID is usually published or calculated based on the Cohen's rule (2). Based on the gMCID and the condition that absolute

value of pMCID is greater than or equal to the absolute value of gMCID, the value of pMCID is derived out. The pMCID for ACQ-5 is derived as -0.5.

• Definition of ACQ-5 responder (based on pMCID): a patient is considered to be a "responder" if his/her change in ACQ-5 score from the baseline in parent study is equal to or greater than the minimal clinically important difference at patient level (pMCID):

Responder = Yes, if change from baseline in ACQ-5 score \leq pMCID;

Responder = No, if change from baseline in ACQ-5 score > pMCID.

Measurement properties such as reliability, ability to detect change have been documented in the literature (3).

Based on the manual of ACQ (4), any more than one missing value is not acceptable. If more than one of the questions have missing value, the global score is invalid and will be considered as missing. If only one question has missing value, it will be interpolated (pro-rated) using the completed questionnaires from the previous visit. For instance, answer to question 5 is missing at Visit 2, and all questions are completed at Visit 1. Then the question 5 score at Visit 2 is interpolated as: (total score at Visit 2/sum of scores of question 1 to question 4 at Visit 1) × score of question 5 at Visit 1. If the questionnaire from the previous visit is not complete either, the missing value will be imputed as the average of the completed questions within the current visit.

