2.1.3.4 Asthma quality of life questionnaire (AQLQ)

The AQLQ was designed to measure the functional impairments that are most troublesome to adults (17 to 70 years) as a result of their asthma (see Appendix G). The instrument is comprised of 32 items, each rated on a 7-point scale from 1 (severely impaired) to 7 (not impaired). The AQLQ has 4 domains. The domains and the number of items in each domain are as follows:

- Symptoms (12 items)
- Activity limitation (11 items)
- Emotional function (5 items)
- Environmental Stimuli (4 items)

The instrument has been used in many clinical trials, and it has been shown to be reliable, valid (patient interviews), and sensitive to change.

Individual items are equally weighted. The overall score is the mean of response to each of the 32 questions. The score of each domain is the mean of response to each question in that domain. Higher scores indicate better quality of life. An MCID is available: the pMCID is approximated to be 0.5 (5).

• Definition of AQLQ responder (based on pMCID): a patient is considered to be a "responder" if his/her change in AQLQ overall score from the baseline in parent study is equal to or greater than the minimal clinically important difference at patient level (pMCID):

Responder = Yes, if change from baseline in AQLQ overall score \geq pMCID;

Responder = No, if change from baseline in AQLQ overall score < pMCID.

To have a valid overall score, it is not acceptable to have more than three missing responses or more than one missing response per domain. For the symptoms and activity limitation domain score, only one missing value per domain is acceptable. For the emotional function and environmental stimuli domain scores, no missing value is acceptable. For responses with intolerable amount of missing value(s), the overall or the domain score will be considered as missing. For the other case, the missing score will be interpolated using the previous completions of the questionnaire following the similar algorithm used for ACQ-5.

The analysis for AQLQ in LTS12551 study will exclude the patients enrolled from the PDY14192 study, as the AQLQ is not assessed in the PDY14192 study.

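### The ACQ-5 rule for a single missing item is undefined when the other four previous items are all 0, and it can return item and global scores above 6

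*SAP*

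**What the plan says.** SAP 2.1.3.3 sets the scale: patients "respond to the symptom questions on a 7-point scale (0=no impairment, 6= maximum impairment"), and "the ACQ-5 score is the mean of the 5 questions and, therefore, between 0 (totally controlled) and 6 (severely uncontrolled").

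The same section then handles missing items. More than one missing item makes the global score missing. For a single gap: "If only one question has missing value, it will be interpolated (pro-rated) using the completed questionnaires from the previous visit". In the SAP's example, with question 5 missing at Visit 2, the value is a ratio, "total score at Visit 2/sum of scores of question 1 to question 4 at Visit 1", multiplied by the question 5 score at Visit 1.

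A fallback follows, with one trigger: "If the questionnaire from the previous visit is not complete either, the missing value will be imputed as the average". The average meant is over the questions answered at the current visit ("the missing value will be imputed as the average of the completed questions within the current visit").

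SAP 2.1.3.4 carries the method to AQLQ, whose items run from 1 to 7. Where the amount missing is tolerable, the score is "interpolated using the previous completions of the questionnaire following the similar algorithm used for ACQ-5".

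Neither section has a rule for a zero denominator or a limit on the imputed value. The general data-handling text in SAP 2.5.2 and 2.5.3 does not add one, and protocol 9.2.2.2 gives no ACQ-5 imputation rule.

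**The concern.** The formula divides by the sum of four items that may all legitimately be 0. That pattern belongs to a well-controlled patient, and such a form is complete, so the fallback is not triggered. When the previous sum is small but not zero, the ratio is unstable and nothing keeps the result on the 0 to 6 scale.

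ACQ-5 score and responder status are listed endpoints (SAP 2.1.3), and ACQ-5 is one of the variables chosen for subgroup analysis (SAP 2.4.4.1). SAP 2.4.4 reports mean, SD and maximum on observed cases, so an impossible value would appear in a table. Without a written rule, whoever programs the endpoint must choose between setting the score missing, capping it or averaging, with open-label data already in hand.

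**Working it through.** The documents give no numerical result for this rule, so there is no figure to reproduce. The check applies the formula as written.

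**Inputs (SAP 2.1.3.3).** Items 0 to 6; global score is the mean of 5 items; responder if the change from parent-study baseline is -0.5 or lower. Notation: P = previous-visit sum of the other four items; q = previous value of the missing item; C = current sum of the four answered items. I read the current total score as C.

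- Interpolated item = (C / P) × q
- Fallback item = C / 4
- Global score = (C + item) / 5

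**Zero denominator.** P = 0 gives C/0, or 0/0 if C is also 0. The previous form is complete, so the fallback does not apply.

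**Item above 6.** P = 4, q = 4, C = 8:

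- Interpolation: 8/4 × 4 = 8; global score (8 + 8)/5 = 3.2
- Fallback: 8/4 = 2; global score (8 + 2)/5 = 2.0
- Difference between methods: 1.2

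With a score of 2.0 the patient is a responder if baseline is at least 2.5; with 3.2, only if baseline is at least 3.7. Any baseline from 2.5 to just below 3.7 is classified differently by the two methods.

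**Global score above 6.** P = 4, q = 4, C = 16: item 16/4 × 4 = 16; global score (16 + 16)/5 = 6.4. At the extreme, P = 1, q = 6, C = 24: item 144; global score (24 + 144)/5 = 33.6.

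**Full enumeration.** Nine items with seven levels give 7^9 = 40,353,607 combinations. Of these, 7^5 = 16,807 have P = 0; 6,457,480 (16.0%) give an item above 6; and 752,542 (1.9%) give a global score above 6. Each combination counts equally here, so these are not expected frequencies. They show only that the out-of-range region is not confined to one contrived case.

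**Alternative reading.** If the current total score means the mean of the answered items, P = 0 is still undefined and the largest item is 6/1 × 6 = 36.

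**AQLQ.** Items start at 1, so the denominator cannot be 0. Assume the ratio is taken within a domain, which the SAP does not state. In the 12-item symptoms domain, let the other 11 items be 2 each before (sum 22) and 5 each now (sum 55), with a previous item of 4:

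- Interpolation: 55/22 × 4 = 10, above 7
- Within-domain mean: 55/11 = 5
- Effect on the overall score: (10 - 5)/32 = 0.16

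One item would have to shift by 0.5 × 32 = 16 points to move the overall score by the 0.5 responder threshold. Values below 1 are also possible: 11/77 × 1 = 0.14.

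**The case against.** The strongest reply concerns materiality. The primary endpoint is TEAEs. ACQ-5 and AQLQ are secondary, with no confirmatory analysis. The rule operates only when exactly one ACQ-5 item is missing, and a programmer could settle the edge cases. All of that stands and limits the point to a minor one. It does not repair the rule, which gives no value or an impossible value for valid input.

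Several stronger readings are tempting, and the documents do not support them:

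- **That the within-visit mean is more accurate and should replace the interpolation throughout.** Which method is closer depends on whether patients keep a stable pattern across items, which the interpolation preserves and the mean ignores. The documents have no data on this, and the SAP says its approach to missing items is based on the ACQ manual.
- **That a known share of records is affected.** The documents give no rate of single missing items and no item-level distribution.
- **That 1.2 points is an error.** It is a difference between two imputations; the true answer is unknown.
- **That a zero denominator flips responder status.** With no value, the record would simply drop out of an observed-case summary. Only inflated values can change responder status, and then only for some baselines.
- **That the previous visit is always 24 weeks old.** That fits the schedule after Amendment 04, with ACQ-5 at Weeks 0, 24 and 48. SAP 1.6 records that the amendment reduced the frequency, so data collected before it had shorter gaps. A long gap is in any case not an arithmetic fault.
- **That AQLQ shares the whole fault.** Only the range problem carries over, and one item is diluted over 32.

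**Conclusion.** The concern holds as a fault in a stated formula. The ACQ-5 interpolation has no value when the other four items on a complete previous form are all 0. It can also return items above 6 and global scores above 6, contradicting the range given in the same section. In the worked case the score is 3.2 against 2.0 with the SAP's own fallback, a between-method difference larger than the 0.5 threshold. For AQLQ the fault is limited to items outside 1 to 7, and the worked case moves the overall score by 0.16.

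This rests on reading the current total score as the sum of the answered items; the zero denominator and the range problem survive the other reading. The AQLQ example also assumes a within-domain ratio. The effect on reported results cannot be sized, because the number of forms with one missing item is not given, and it is confined to descriptive secondary endpoints. Nothing here touches the safety conclusions.

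**What to change.** Add one sentence to SAP 2.1.3.3: if the previous-visit sum of the other four items is 0, or the interpolated item falls outside 0 to 6, impute the item with the existing fallback, the mean of the items answered at the current visit. Add a matching sentence to SAP 2.1.3.4: if the interpolated AQLQ item falls outside 1 to 7, use the mean of the answered items in the same domain at the current visit. Keep the interpolation in all other cases. It would help to state in the same place that the current total score is the sum of the answered items.

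The cost is two sentences and a small programming change, with no new data or method. The fallback is always defined and always on the scale. The trade-off is a departure from the interpolation in the flagged records; whether the cited ACQ manual already covers them cannot be checked from the documents. The guard leaves large but in-range interpolated values as they are, which is the price of keeping the SAP's chosen method.

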2.1.3.4 Asthma quality of life questionnaire (AQLQ)

The AQLQ was designed to measure the functional impairments that are most troublesome to adults (17 to 70 years) as a result of their asthma (see Appendix G). The instrument is comprised of 32 items, each rated on a 7-point scale from 1 (severely impaired) to 7 (not impaired). The AQLQ has 4 domains. The domains and the number of items in each domain are as follows:

- Symptoms (12 items)
- Activity limitation (11 items)
- Emotional function (5 items)
- Environmental Stimuli (4 items)

The instrument has been used in many clinical trials, and it has been shown to be reliable, valid (patient interviews), and sensitive to change.

Individual items are equally weighted. The overall score is the mean of response to each of the 32 questions. The score of each domain is the mean of response to each question in that domain. Higher scores indicate better quality of life. An MCID is available: the pMCID is approximated to be 0.5 (5).

• Definition of AQLQ responder (based on pMCID): a patient is considered to be a "responder" if his/her change in AQLQ overall score from the baseline in parent study is equal to or greater than the minimal clinically important difference at patient level (pMCID):

Responder = Yes, if change from baseline in AQLQ overall score \geq pMCID;

Responder = No, if change from baseline in AQLQ overall score < pMCID.

To have a valid overall score, it is not acceptable to have more than three missing responses or more than one missing response per domain. For the symptoms and activity limitation domain score, only one missing value per domain is acceptable. For the emotional function and environmental stimuli domain scores, no missing value is acceptable. For responses with intolerable amount of missing value(s), the overall or the domain score will be considered as missing. For the other case, the missing score will be interpolated using the previous completions of the questionnaire following the similar algorithm used for ACQ-5.

The analysis for AQLQ in LTS12551 study will exclude the patients enrolled from the PDY14192 study, as the AQLQ is not assessed in the PDY14192 study.

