- h Spirometry should be done at the study site approximately the same time of the day (preferably in the morning, but it could be done at a different time of the day). Spirometry will be performed after a washout period of bronchodilators according to their action duration (for example, withholding the last dose of salbutamol/albuterol or levosalbutamol/levalbuterol for at least 6 hours and withholding the last dose of LABA for at least 12 hours [ultra-LABA like vilanterol should be withheld for at least 24 hours] and withholding the last dose of LAMA for at least 24 hours). Also spirometry should be performed prior to IMP administration, as applicable.
- i ACQ-5 and AQLQ(S) paper forms are completed during clinic visits. Data will be collected into the e-CRF. Note: For patients from PDY14192 study, AQLQ(S) paper form must be completed at the Combined V1/V2 Visit as part of the LTS12551 assessments.
- j A questionnaire of health care resource utilization (reliever medication, specialist visit, hospitalization, emergency or urgent medical care facility visit, outcome, sick leaves, etc). Data will be collected into the e-CRF.
- k Vital signs: blood pressure (mmHg), heart rate (beats per minute), respiratory rate (breaths per minute), body temperature (degrees Celsius), and body weight (kg) will be measured at each visit. Height (cm) will only be measured at the Enrollment (Combined V1/V2) Visit. Vital signs will be measured in the sitting position using the same arm at each visit and will be measured prior to IMP administration at the clinic visits.

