- h* Spirometry should be done at the study site approximately the same time of the day (preferably in the morning, but it could be done at a different time of the day). Spirometry will be performed after a washout period of bronchodilators according to their action duration (for example, withholding the last dose of salbutamol/albuterol or levosalbutamol/levalbuterol for at least 6 hours and withholding the last dose of LABA for at least 12 hours [ultra-LABA like vilanterol should be withheld for at least 24 hours] and withholding the last dose of LAMA for at least 24 hours). Also spirometry should be performed prior to IMP administration, as applicable.
- i* ACQ-5 and AQLQ(S) paper forms are completed during clinic visits. Data will be collected into the e-CRF. Note: For patients from PDY14192 study, AQLQ(S) paper form will be completed at the Combined V1/V2 Visit.
- j* A questionnaire of health care resource utilization (reliever medication, specialist visit, hospitalization, emergency or urgent medical care facility visit, outcome, sick leaves, etc). Data will be collected into the e-CRF.
- k* Vital signs: blood pressure (mmHg), heart rate (beats per minute), respiratory rate (breaths per minute), body temperature (degrees Celsius), and body weight (kg) will be measured at each visit. Height (cm) will only be measured at the Enrollment (Combined V1/V2) Visit. Vital signs will be measured in the sitting position using the same arm at each visit and will be measured prior to IMP administration at the clinic visits.

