- Administer paper ACQ-5, AQLQ(S), and health care resource utilization questionnaire. Note: For patients coming from Study PDY14192, AQLQ(S) is not obtained from the parent study, so those patients will have to complete the paper questionnaire at the Combined V1/V2 Visit in LTS12551 study.
- Spirometry:
 - Spirometry will be performed after withholding the last dose of salbutamol/albuterol or levosalbutamol/levalbuterol for at least 6 hours, the last dose of LABA for at least 12 hours (ultra-LABA like vilanterol should be withheld for at least 24 hours) and the last dose of LAMA for at least 24 hours, and prior to the administration of IMP. This will be verified before performing the measurements.
- Perform 12-lead ECG.
- Collect blood samples for the following (fasting - overnight fast or minimum of 8 hours fast):
 - Hematology: Blood count (erythrocytes, hemoglobin, hematocrit, leukocytes), differential blood count (neutrophils, lymphocytes, monocytes, eosinophils, basophils), and platelets.
 - Serum chemistry: Total bilirubin (in case of values above the normal range, differentiation in conjugated and non-conjugated bilirubin), ALT, AST, ALP, total protein, albumin, total cholesterol, CPK, glucose, creatinine, BUN, uric acid, bicarbonate, and electrolytes (sodium, potassium, chloride).

- Serology: HBsAg, hepatitis B surface antibody (HBsAb), HBcAb, total HBcAb, HCV Ab, HIV screen (Anti-HIV-1 and HIV-2 antibodies) and ANA; (these tests were scheduled at the visit prior to the *end-of-treatment visit of the PDY14192, EFC13579 or EFC13691 parent studies*). In addition, results from HBV DNA testing and HCV virus RNA (HCV RNA) testing should be collected for those patients who were HBsAg negative and HBcAb positive, and/or HCV Ab positive; also anti-double-strand DNA antibody results for patients with ANA positive ($\geq 1:160$ titer).
- Serum sample for PK and ADA (before dose of IMP).
- Eosinophil count (derived from clinical laboratory test).
- [REDACTED]
- Urine for urinalysis (dipstick) (see [Section 9.2.1.4](#)).
- Urine pregnancy test (for women of childbearing potential).

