10.1.1.10 Visit 11 (Month 6, Week 24)

- Record all medication use with start dose in e-CRF including starting dose.

- Inquire about AEs/SAEs and background asthma therapy tolerability.
- Measure vital signs (blood pressure, heart rate, respiration rate, body temperature, weight).
- Perform physical examination.
- Administer paper ACQ-5, AQLQ(S), and health care resource utilization questionnaire.
- Perform spirometry:
 - Spirometry will be performed after withholding the last dose of salbutamol/albuterol or levosalbutamol/levalbuterol for at least 6 hours and withholding the last dose of LABA for at least 12 hours (ultra-LABA like vilanterol should be withheld for at least 24 hours) and withholding the last dose of LAMA for at least 24 hours prior to administration of investigational product. This will be verified before performing the measurements.
- Perform 12-lead ECG.
- Perform blood sampling for:
 - Clinical laboratories.
 - Serum sample (predose) for PK and anti-dupilumab antibody analysis.
 - Hepatitis B viral load testing: For patients in Japan (or other countries/regions if there is local regulatory requirement) who were HBsAg negative and HBsAb positive at screening during the parent study, or at the additional test due to Local Amendment 03 (Japan).
- Perform urine pregnancy test (for women of childbearing potential).
- Obtain urine for urinalysis (dipstick).
- Call IVRS/IWRS to register visit and obtain treatment kits' numbers.
- Dispense and administer IMP:
 - Patients will be monitored at the study site for a minimum of 30 minutes after the injection.
 - After Week 12, for patients (or parents caregivers) unable or unwilling to self-administer IMP, arrangements must be made for the patient to receive IMP injections at the study site as unscheduled visits, or for qualified site personnel and/or a professional caregiver to administer IMP at home at q2w intervals.
- Remind patient to continue the background therapy and schedule appointment for next visit.
- Perform monthly telephone contact with patient after Week 24 (Visit 11) to collect safety information.

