10.1.2.12 Visit 17 (End-of-Treatment: Month 12, Week 48)

End-of-Treatment visit is scheduled 2 weeks after the last IMP administration.

- Record all medication use with start dose in e-CRF including starting dose.
- Inquire about AEs/SAEs and background asthma therapy tolerability.
- Measure vital signs (blood pressure, heart rate, respiration rate, body temperature, weight).
- Perform physical examination.
- Administer paper ACQ-5 and AQLQ(S).
- Administer health care resource utilization questionnaire.
- Perform spirometry:
 - Spirometry will be performed after withholding the last dose of salbutamol/albuterol or levosalbutamol/levalbuterol for at least 6 hours and withholding the last dose of LABA for at least 12 hours (ultra-LABA like vilanterol should be withheld for at least 24 hours) and withholding the last dose of LAMA for at least 24 hours prior to administration of investigational product. This will be verified before performing the measurements.
- Perform 12-lead ECG.
- Perform blood sampling for:
 - Clinical laboratories.
 - Serum sample (predose) for PK and anti-dupilumab antibody analysis.
 - Hepatitis B viral load testing: For patients in Japan (or other countries/regions if there is local regulatory requirement) who were HBsAg negative and HBsAb positive at

screening during the parent study, or at the additional test due to Local Amendment 03 (Japan).

- [REDACTED]
- Perform urine pregnancy test (for women of childbearing potential).
- Obtain urine for urinalysis (dipstick).
- Call IVRS/IWRS to register the EOT date.
- Schedule appointment for next visit and remind patient to withhold the last dose of salbutamol/albuterol or levosalbutamol/levalbuterol for at least 6 hours and withholding the last dose of LABA for at least 12 hours (ultra-LABA like vilanterol should be withheld for at least 24 hours) and withholding the last dose of LAMA for at least 24 hours prior to the next visit.
- Remind patient to continue the background therapy.
- Remind patients to arrive for next visit in fasting state.
- Perform monthly telephone contact with patient after Week 24 (Visit 11) to collect safety information.

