Appendix B Summary of statistical analyses

EFFICACY ANALYSIS

Endpoint	Analysis population	Primary analysis	Statistical Method	Supportive analysis	Subgroup analysis	Other analyses
FEV1, % Predicted FEV1, FVC and FEF 25-75%	Safety	Measurement and change from baseline at all visits	Descriptive statistics	No	Yes (Baseline ICS dose and EOS count subgroups)	No
Severe exacerbation: number of events/annualized event rate during the treatment period	Safety	Summary of number/annualized rate of severe exacerbation events during the treatment period	Descriptive statistics	No	Yes (Baseline ICS dose and EOS count subgroups)	No
Morning asthma symptom score	Safety	Measurement and change from baseline at all visits, for patients from the DRI12544 study only	Descriptive statistics	No	No	No
Evening asthma symptom score	Safety	Measurement and change from baseline at all visits, for patients from the DRI12544 study only	Descriptive statistics	No	No	No
ACQ-5 score	Safety	Measurement, change from baseline, and responder status at all visits	Descriptive statistics	No	Yes (Baseline ICS dose and EOS count subgroups)	No
AQLQ overall score	Safety	Measurement, change from baseline, and responder status at all visits, excluding patients from the PDY14192 study	Descriptive statistics	No	Yes (Baseline ICS dose and EOS count subgroups)	No
AM PEF	Safety	Measurement and change from baseline at all visits, for patients from the DRI12544 study only	Descriptive statistics	No	No	No
PM PEF	Safety	Measurement and change from baseline at all visits, for patients from the DRI12544 study only	Descriptive statistics	No	No	No
Number of inhalations/day of	Safety	Measurement and change from baseline at all visits, for patients from the DRI12544 study only	Descriptive statistics	No	No	No

Statistical Analysis Plan	20-Jul-2017
SAR231893-LTS12551 - dupilumab	Version number: 3

Endpoint	Analysis population	Primary analysis	Statistical Method	Supportive analysis	Subgroup analysis	Other analyses
reliever medication						
Number of nocturnal awakenings	Safety	Measurement and change from baseline at all visits, for patients from the DRI12544 study only	Descriptive statistics	No	No	No
EQ-5D-3L single utility score and VAS	Safety	Measurement and change from baseline at all visits, for patients from the DRI12544 study only	Descriptive statistics	No	No	No

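### The SAP drops PDY14192 patients from every AQLQ summary, but its reason covers only change from the parent-study baseline and responder status

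*SAP*

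**What the plan says.** **Exclusion.** SAP 2.1.3.4 states: "The analysis for AQLQ in LTS12551 study will exclude the patients enrolled from the PDY14192 study, as the AQLQ is not assessed" in PDY14192. Appendix B shows how far this reaches. The AQLQ row reads: "Measurement, change from baseline, and responder status at all visits, excluding patients from the PDY14192 study".

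**Baseline and responder rule.** Protocol 11.4.2 and SAP 2.1.3 and 2.4.4 take the parent-study baseline as the efficacy baseline. SAP 2.1.3.4 defines an AQLQ responder as a patient whose overall score has risen by at least 0.5 from that baseline.

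**Collection at Week 0.** Footnote i of the protocol flow chart in Section 1.2 says: "For patients from PDY14192 study, AQLQ(S) paper form must be completed at the Combined V1/V2 Visit as part of the LTS12551 assessments". The same footnote in Section 1.3 says: "For patients from PDY14192 study, AQLQ(S) paper form will be completed at the Combined V1/V2 Visit". Protocol 10.1.1.1 explains that the parent study does not supply the score, so "those patients will have to complete the paper questionnaire at the Combined V1/V2 Visit in LTS12551 study". Section 10.1.2.1 repeats the requirement for patients enrolled after Amendment 04.

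**Collection afterwards.** At Week 24 the instruction for all patients is "Administer paper ACQ-5, AQLQ(S), and health care resource utilization questionnaire" (protocol 10.1.1.10 and 10.1.2.10). Week 48 also includes AQLQ(S) (10.1.1.12 and 10.1.2.12). No parent study is exempted.

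**Population and display.** Protocol 11.4.2 and SAP 2.4.4 analyse efficacy on the safety population as observed cases. SAP 2.3.2 presents each planned analysis for non-OCS patients by parent study, and by Placebo/Dupilumab and Dupilumab/Dupilumab within each.

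**The concern.** The protocol adds a questionnaire for one group of patients because their parent study had none, and follows them with the same instrument for a year. The SAP then gives the same gap in the parent study as its reason to leave them out of every AQLQ summary, including those that use no parent-study value.

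AQLQ(S) is a named secondary endpoint, and the SAP lists it among its key efficacy variables for subgroup analysis (2.4.4.1). As written, patients fill in a 32-item form at three visits and nothing is reported from it. The PDY14192 columns for AQLQ are blank.

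**Working it through.** **Step 1. The plan's own total.** Parent-study sizes from SAP 1.1 are DRI12544 776, EFC13579 1902, EFC13691 210 and PDY14192 42 (planned).

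- 776 + 1902 + 210 + 42 = 2930, which reproduces the maximum in SAP 1.3.
- Non-OCS population (all but EFC13691): 2930 − 210 = 2720.

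**Step 2. Size of the excluded group, at most.**

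- Share of all patients: 42 / 2930 = 1.4%.
- Share of non-OCS patients: 42 / 2720 = 1.5%.
- Share of the approximately 2206 patients in the protocol synopsis: 42 / 2206 = 1.9%.
- Per prior arm under 1:1 randomisation: 42 / 2 = 21.
- AQLQ set with the exclusion: 2930 − 42 = 2888 overall, and 2720 − 42 = 2678 non-OCS.
- Scheduled forms (Weeks 0, 24 and 48): 42 × 3 = 126 if all roll over, and 21 × 3 = 63 if half do. Both rollover rates are assumptions, because the documents give none.

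**Step 3. Each AQLQ summary in Appendix B against the stated reason.**

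- *Measurement at each visit.* It needs only the score at that visit. Protocol 11.4.2 and SAP 2.4.4 both plan the parameter itself as well as its change. The data exist at Weeks 0, 24 and 48, so the reason does not apply.
- *Change from baseline.* It needs a parent-study score, and PDY14192 has none. The reason applies.
- *Responder status.* It is defined on that change. The reason applies.

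**Step 4. Whether the SAP can already place these scores.** SAP 2.1 defines Week 0 as the last measurement before the first LTS12551 dose when no parent-study visit value is available. Table 6 gives AQLQ a Week 0 window as well as Week 24 and Week 48 windows. No new derivation is needed for observed scores.

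**Step 5. Whether another reason is given.** SAP 1.6 restricts the diary, EQ-5D-3L and immunoglobulin analyses to DRI12544 because collection stopped and the other studies had little data. That does not carry over: AQLQ(S) remains on both flow charts after Amendment 04.

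**The case against.** The exclusion is stated openly, with its reason, in two places, and protocol 11.4.2 leaves efficacy detail to the SAP. The reason is sound for two of the three Appendix B summaries. Protocol 11.4.5 describes the AQLQ(S) analysis as change from baseline, which these patients cannot contribute. The group is small, the endpoint is descriptive, and the primary objective is safety. All of this stands, and it limits the weight of the point. It does not explain why observed scores are dropped too.

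A reader might go further and infer that LTS12551 Week 0 can serve as the baseline for all PDY14192 patients, so that change and responder status could be restored in full. The documents do not support that.

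- Dupilumab/Dupilumab patients have already had 12 weeks of treatment by Week 0 (SAP 1.1). A patient who simply holds an earlier gain would count as a non-responder, next to columns measured from a pre-treatment baseline.
- For Placebo/Dupilumab patients, Week 0 does precede dupilumab, but it is the PDY14192 end-of-treatment visit. SAP 1.1 places a bronchoscopy at the end of that treatment period, followed by 3 (up to 5) days of oral prednisone. The documents do not say how the form is timed relative to either, so Week 0 may not be an undisturbed baseline.
- The SAP plans no change from Week 0 in AQLQ for any parent study. Version 3 altered its layouts to avoid confounding from between-study variation, and pooling two kinds of baseline would work against that.

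A reader might also infer that the Week 0 form serves no purpose. The protocol does not state what it is for, so that cannot be concluded.

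**Conclusion.** The point holds in a limited form. The SAP's reason justifies leaving PDY14192 patients out of change from the parent baseline and responder status. It does not justify leaving them out of the by-visit summaries of observed AQLQ scores, which both documents plan on the safety population.

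The effect on pooled results is minor: at most 1.4% of all patients or 1.5% of the non-OCS population, and no primary result changes. The effect on the by-parent-study display is complete, since PDY14192 would have no AQLQ result. The figure of 42 is an upper bound. It is the planned parent-study size, rollover is not given, and protocol 9.2.2.4 uses the questionnaire only where a validated translation exists.

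**What to change.** - In SAP 2.1.3.4, limit the exclusion to change from the parent-study baseline and the responder status defined on it.
- Include PDY14192 patients in the by-visit summaries of observed AQLQ scores at Weeks 0, 24 and 48, by Placebo/Dupilumab and Dupilumab/Dupilumab.
- Align the AQLQ row in Appendix B, where "excluding patients from the PDY14192 study" now covers all three summaries. State whether the ICS-dose and eosinophil subgroup tables follow the same rule.
- Optionally, add change from Week 0 for Placebo/Dupilumab patients only. Label it as Week 0-based and descriptive, with a note that Week 0 falls at the PDY14192 end-of-treatment visit, near a bronchoscopy and a short oral prednisone course. Do not report a Week 0-based responder rate for Dupilumab/Dupilumab patients, and do not pool Week 0-based change into the All column.

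If the sponsor prefers to keep the full exclusion, the SAP should say why the observed scores are not reported.

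The cost is SAP wording and small additions to existing tables; no new data are needed. The one drawback is that patient numbers will differ between the observed-score and change-from-baseline summaries, which a footnote can explain.
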